We will assess the association between maternal weight trajectories and childhood asthma at age 4 or 5 using logistic regression, limited to the children with data at ages 4 or 5 years. Multivariable logistic regression models will adjust for similar covariates to those described above for the obesity analyses.

Methods to address error in variables: We anticipate there being a moderate number of errors in weight measurements, primarily due to measurement error, but some also due to recording errors. We anticipate that date of birth will be largely accurate in the EHR, but that other dates and clinical events will be prone to errors. Some of the covariates (specifically, race, diabetes, tobacco use, and medications) are known to be particularly error-prone, and we anticipate that patient records with errors in one variable will tend to be more likely to have errors in multiple variables. We also anticipate a moderate number of errors in the linkage of maternal-child records.

We will implement a multi-wave, targeted validation sub-study; the validation strategy is outlined in the next section. Once we have obtained validation data for a subsample of patient records, we will perform the proposed study analyses highlighted above but augmented using specific methods to incorporate both the validated and unvalidated data. We will consider multiple analysis approaches as what is optimal for the problem may depend on the error structure. Namely, we will consider a maximum likelihood, multiple imputation, and generalized raking approaches. The optimal raking variable will be constructed using multiple imputation, as described in Han et al. (2019). Single imputation methods, such as regression calibration, in combination with raking will also be considered (Oh et al., 2019) These methods will take into account the targeted nature of the validation sample (i.e., the fact that the

validation sample is not a completely random sample, but rather a targeted random sample [e.g., weighted or stratified sampling] in the first and second validation waves).

Data Validation Strategy

Our goal will be to optimize the information learned (i.e., minimize variance of corrected estimates) based on our budgetary constraints; we anticipate we will be able to validate between 500-1000 records.

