Data validators will receive validation training from Drs. [name], [name], and [name], and will enter validation data into standardized REDCap validation forms built off of the PCORnet Common Data Model. We anticipate validation that will happen in 2 waves. The first wave will be treated as a pilot sample and information learned regarding data discrepancies will be used to tailor the individuals selected in the second validation wave.

We will design our multi-wave validation sampling with two separate analyses in mind: (1) association between maternal weight change during pregnancy and time to childhood obesity and (2) association between maternal weight change during pregnancy and probability of asthma for child. We will design our validation sample such that we develop two separate sampling schemes to optimize these two separate analyses. As childhood obesity is our primary endpoint, approximately 2/3 of our chart reviews will be targeted towards this endpoint, the other 1/3 will be targeted towards childhood asthma. Naturally, the charts that are targeted for validation to improve estimation of the childhood obesity outcome will still be used for the childhood asthma analyses and vice versa, even though they are not targeted for that purpose.

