For the first wave of validation sampling, no more than half of the records will be sampled according a balanced stratified sample, with randomly selected samples within strata. For the childhood obesity endpoint, we will create 6 strata based on all combinations of obesity (yes/no) and rate of maternal weight gain ($\leq 25^{\text{th}}$ percentile, $25^{\text{th}}\text{-}75^{\text{th}}$ percentile, $>75^{\text{th}}$ percentile). In wave 1 of chart validation, we will validate 40 charts per stratum (total of 240 charts). For the asthma endpoint, we will create 6 strata based on all combinations of childhood asthma (yes/no) and rate of maternal weight gain ($\leq 25^{\text{th}}$ percentile, $25^{\text{th}}\text{-}75^{\text{th}}$ percentile, $>75^{\text{th}}$ percentile); note that the only patients included in these analyses will be those children followed with at least one visit from ages 4-5 years. In wave 1, we will validate 25 charts per stratum (total of 150). Therefore, our first wave of chart reviews will include a total of 390 charts. For the chosen records, validation will be performed by going through the entire EHR (free text and other fields not part of the PCORnet Common Data Model) to validate key study variables, which include the primary outcomes, exposures, and key covariates given above. De-identified validation data will be securely transferred to study investigators (Drs. [name] and [name]) who will then use this information to tailor a second wave of data validation.

For the second wave of validation, we anticipate over-sampling/targeting records that are more influential, such as those that appear to be more prone to errors (based on our initial wave of data validation), records that are more likely to have observed events, and records with extreme values or influence on the estimating equations. We plan to target our samples to

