minimize the variance of the estimate of our primary outcome (time-to-obesity) and secondary outcome (incidence of asthma). Hence, we plan to sample following adaptations of the mean-score sampling approach of McIsaac and Cook (2015) to optimize sampling for the discrete proportional hazards and logistic regression models. Neyman allocation strategies will be employed to assure efficiency and to guarantee sufficient information per stratum so that all analysis methods may be employed. If the first wave reveals a large amount of outcome misclassification, then these methods may be adjusted so as stratify on predicted true positive versus predicted true negative results, versus the error prone outcome alone in the second wave. For example, rather than sampling based on influence functions plugging in the phase 1 data, we may sample based on influence functions plugging in multiply imputation estimators based on the wave 1 validation. We anticipate validating several hundred additional records for this wave 2 validation; hopefully at least as many as in the wave 1 validation. Exact numbers to validate will be determined based on feasibility and costs learned from the wave 1 validation. Data from this second wave of validation will be similarly entered into REDCap and transferred to study investigators.

References

Han K, [name] PA, Lumley T. Combining multiple imputation with raking of weights in the setting of nearly-true models. (arXiv:1910.01162[stat.ME])

Oh E, [name] BE, Lumley T, [name] PA. Raking and Regression Calibration: Methods to Address Bias from Correlated Covariate and Time-to-Event Error. (arXiv:1905.08330v1 [stat.ME])

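### Does a first validation wave fixed at 390 charts break the plan's own half rule when 500 to 1000 charts are expected?

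*Combined protocol and SAP*

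**What the plan says.** All the relevant text is in section 5.1 of the combined protocol and SAP, mostly under Data Validation Strategy.

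- Expected total: "we anticipate we will be able to validate between 500-1000 records".
- Limit on the first wave: "For the first wave of validation sampling, no more than half of the records will be sampled according a balanced stratified sample".
- Size of the first wave: six obesity-by-weight-gain strata of 40 charts and six asthma-by-weight-gain strata of 25, so that "our first wave of chart reviews will include a total of 390 charts".
- Split between endpoints: "approximately 2/3 of our chart reviews will be targeted towards this endpoint, the other 1/3 will be targeted towards childhood asthma". The same paragraph adds that charts chosen for one endpoint also serve the analysis of the other.
- Second wave: "We anticipate validating several hundred additional records for this wave 2 validation; hopefully at least as many as in the wave 1 validation". The next sentence leaves the final count to the cost and feasibility seen in wave 1.
- Allocation in the second wave: "Neyman allocation strategies will be employed to assure efficiency and to guarantee sufficient information per stratum".
- Analysis (under methods to address error in variables): "These methods will take into account the targeted nature of the validation sample", with both waves named.

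**The concern.** The plan gives a ceiling as a fraction and a wave 1 size as a number, and the two agree over only part of the expected range of totals. The ceiling is worded as a rule, while the condition that would satisfy it, a second wave no smaller than the first, is worded as a hope. Nothing scales wave 1 down for a small budget, and the total is settled only after the 390 charts have been reviewed.

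What would be at stake is the adaptive part of the design. The stated goal is to minimise the variance of the corrected estimates within budget, and the second wave is where charts are steered towards the most informative strata. If wave 1 used most of a small budget, little would be left to steer, and the asthma sample, with the smaller share, would have the least room.

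**Working it through.** **Inputs (all from section 5.1).** Obesity: 6 strata × 40 charts. Asthma: 6 strata × 25 charts. Expected total: 500 to 1000. Limit: one half. Endpoint split: about 2/3 to 1/3.

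**The plan's own figure.** 6 × 40 = 240; 6 × 25 = 150; 240 + 150 = 390. The stated total is reproduced.

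**Total needed to meet the limit.** 390 / T ≤ 1/2 gives T ≥ 780. This reads the limit as a share of all validated records, which the text does not spell out but is the natural meaning, and assumes no child is drawn for both samples.

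| Total T | Wave 1 share (390/T) | Left for wave 2 (T − 390) |
|---|---|---|
| 500 | 78.0% | 110 |
| 600 | 65.0% | 210 |
| 690 | 56.5% | 300 |
| 780 | 50.0% | 390 |
| 1000 | 39.0% | 610 |

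Totals of 500 to 779 exceed the limit; totals of 780 to 1000 meet it. The hoped-for second wave of at least 390 gives 390 + 390 = 780, exactly the threshold.

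**Overlap.** The documents give no overlap figure. If d charts served both samples, the threshold would be 2 × (390 − d): 680 for d = 50, 580 for d = 100 and 500 for d = 140. Only an overlap of about 140 of the 150 asthma charts would clear the whole range, so overlap is unlikely to explain the mismatch.

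**Asthma-targeted charts left at a total of 500.** The answer depends on how the approximate split is applied.

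- Exactly 1/3: 500/3 ≈ 167; 167 − 150 = 17 left. A stratum could end with 25 to 25 + 17 = 42 charts, or 15% to 25% of 167.
- Wave 1's own ratio: 150/390 = 38.5%; 0.385 × 500 ≈ 192; 192 − 150 = 42 left. A stratum could end with 25 to 25 + 42 = 67 charts, or 13% to 35% of 192.

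The corresponding remainders at a total of 600 are 200 − 150 = 50 and 231 − 150 = 81. These counts exclude obesity-targeted charts, which also inform the asthma analysis.

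**What a smaller wave 1 would cost.** To respect the limit at 500, wave 1 could be 6 × 25 + 6 × 16 = 246 charts (246/500 = 49.2%), leaving 254. The standard error of a stratum error rate, √(p(1 − p)/n), then rises by √(40/25) = 1.26 for obesity and √(25/16) = 1.25 for asthma. At an assumed 20% error rate that is 6.3 to 8.0 and 8.0 to 10.0 percentage points. At 10% it is 4.7 to 6.0 and 6.0 to 7.5; at 30% it is 7.2 to 9.2 and 9.2 to 11.5. Returning every stratum to 40 and 25 in wave 2 would take 390 − 246 = 144 of the 254 charts and leave 110, the same number as under the present plan. If the budget then reached 1000, the pilot would be only 246/1000 = 24.6% of the sample.

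**The case for a change.** The strongest case for a change runs as follows. A ceiling and a hope are different commitments. Even a second wave of 300, one fair reading of several hundred, puts wave 1 at 56.5%. Reviewed charts cannot be reallocated, so the point must be settled before wave 1 begins. A smaller first wave forecloses nothing, because the remaining charts can restore the present stratum sizes, whereas a 390-chart first wave commits them in advance.

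The inconsistency stands, and so does the point about timing. The claim of harm does not get as far. No variance has been computed under either design, and nothing shows that the best allocation would fall outside the range still reachable after 390 charts. If it falls inside, nothing is lost. A smaller pilot also estimates stratum error rates less well, and those estimates guide the second-wave allocation, so the gain in flexibility is paid for with poorer information on how to use it. Sizing wave 1 to the smallest conceivable budget also sits badly with a plan that means to learn feasibility and cost from that wave. Statisticians could reasonably prefer either design.

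**Conclusion.** The half rule and the fixed 390 charts agree only for totals of at least 780, given the natural reading of the denominator and no overlap between the two samples. Below that, the rule is exceeded, by most at a total of 500: 78% in wave 1, with 110 charts left, of which roughly 17 to 42 would be asthma-targeted.

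No change follows. The wave 1 counts are explicit, so the team knows what to draw. The plan's own hope for wave 2 meets the rule, and the final number is openly left until costs are known. The consequence of a low total is a smaller adaptive wave. That brings no bias so long as the analysis uses the actual sampling design, as the plan says it will, and a loss of efficiency has not been demonstrated. Recasting the rule as a target, or naming 780 as the planning minimum, would tidy the text without altering a chart or a result. Shrinking wave 1 is a design preference with its own cost in pilot precision. In practice the half rule can be read as a target that the second-wave sentence already treats as a hope.
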